### 8.3 Tertiary objectives

Tertiary objective	Corresponding tertiary endpoint/outcome variable(s)	Section
•	I. [REDACTED]	9.5.3.3
•	[REDACTED]	
•	[REDACTED]	

[figure not shown]
## 9 DESIGN OF THE CLINICAL INVESTIGATION

### 9.1 General

The investigation is prospective, single-center, comparative investigation with within-subject control design. It is estimated that 12-14 subjects previously implanted with the I1 implant will be fitted with Oticon Medical Sentio 1 sound processor.

The investigation includes two laboratory visits at the research unit at Chalmers tekniska högskola ([name]), with a field trial period between. Both visits will take between 2-3 hours including breaks. At the first visit the subject's current device is evaluated and Sentio 1 is fitted according to the audiological manual [D]. Audiological measurements will be conducted. If needed, finetuning will be applied according to the subject's preference. Retention will be assessed and the magnet in the sound processor will be adjusted according to the investigator judgement and subject needs and preference. The subjects will wear the Sentio 1 in their daily life for 1 month (visit window +1 month). During

the field trial the subjects will fill out one questionnaire. At the second visit, any AE that occurred in the field trial will be evaluated. Audiological measurements will be conducted. If needed, finetuning will be applied according to the subject's preference. Retention will be assessed and the magnet in the sound processor will be adjusted according to the investigator judgement and subject needs and preference. A preference questionnaire will be filled out during the visit. A third and fourth visit are scheduled after one and two years respectively of using the device, with the main purpose to monitor safety using the device. Visit 3 can be conducted at Chalmers or at the Hearing clinic in Gothenburg or as a telephone visit. Visit 4 will take place at the Hearing clinic in Gothenburg.

Due to the nature of the end points (comparisons between aided and unaided, and Sentio 1 and current sound processor) there is no possibility to blind the investigation as the conditions are obvious for the subject.

Enrollment of subjects is expected to occur in the second half of 2022, after approvals from the Ethical Committee (EC) and Regulatory Authority (Läkemedelsverket, LMV). The investigation will be considered completed when the last subject has completed the last visit.

## 9.2 Investigational device(s) and comparator(s)

The investigational device is the Sentio 1, which has been described in section 5. For secondary objectives A1-3 and B1 the subject's own device will be the comparator device.

Each subject will receive one investigational device. Additional spare devices will be available with the investigator in case of subjects losing or breaking a device.

## 9.3 Subjects

Subject previously implanted with the I1 implant will be asked to take part in the study. Recruitment of the patients will be the responsibility of the Principal Investigator (PI).

### 9.3.1 *Inclusion criteria*

Patients meeting following criteria may be included in the investigation:

1. Signed Informed Consent Form
2. Adult subjects (18 years or older)
3. Subjects implanted with an I1 implant
4. Fluent in Swedish

### 9.3.2 *Exclusion criteria*

Subjects meeting any of following criteria will not be permitted to participate in the investigation:

1. Subjects who do not have the ability or are un-willing to follow investigational procedures/requirements, e.g., to complete questionnaires, according to investigator's

oticon MEDICAL	Title Clinical Investigation Plan BC114	Document no Doc-00117705	Revision 4	Page 19(39)
--------------------------	---	------------------------------------	----------------------	-----------------------

discretion.

2. Subject deemed unsuitable for any medical or other reason as judged by PI or medical responsible

#### 9.3.2.1 Relationship of investigation population to target population.

The target population for the Sentio 1 is patients with either a mixed/conductive hearing loss (MHL/CHL) or SSD. In the investigation on the S1 and I1 implant [G] only patients with mixed/conductive losses were included, thus only patients with MHL/CHL will be included in this investigation. No children will be included in this investigation.

#### *9.3.3 Criteria and procedures for subject withdrawal or lost to follow up*

Subjects are free to discontinue participation in the investigation at any time and are not required to give a reason for their decision. This will not affect the future treatment / medical care of the subject. However, subjects who discontinue the investigation should be asked about the reasons(s) for their discontinuation, and about the presence of any adverse event (AE) / adverse device effect (ADE) and if possible, be assessed by an investigator. If such withdrawal is due to problems related to the investigational device safety or performance, the investigator shall ask for the subject's permission to follow his/her status/condition outside the clinical investigation.

Subjects may be withdrawn from further participation in the investigation if the investigator judges that this is in the subject's best interest, or for safety reasons.

Other reasons for premature discontinuation may be severe non-compliance to the CIP as judged by the investigator and/or the Sponsor, or incorrect enrolment, i.e., a subject did not meet the required inclusion/exclusion criteria for the investigation.

Should a subject fail to show up on agreed visits the site personnel should use all reasonable efforts to get in contact with the subject to prevent anyone from being 'lost-to follow-up'. The contact attempts should be properly documented in the subject's medical record.

The investigator will be thoroughly informed at the site initiation training that missing data should be avoided to the farthest extent reasonably possible as it could have deleterious effects on trial integrity and credibility.

Due to the prerequisites for participating in the investigations, subjects withdrawing, discontinuing or being lost to follow-up from the investigation will not be replaced. Collected data will be considered as far as possible in analyses.

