## 11 STATISTICAL DESIGN AND ANALYSIS

The statistical analysis of all efficacy variables will be performed according to the study Statistical Analysis Plan. The general methodology for the analysis of primary, secondary, and tertiary endpoints is described below. Wilcoxon signed-rank test will be used to test hypotheses. The decision of the hypothesis test is done at the 5% significance level. Pearson's correlations (or Spearman's if the data is not normally distributed) will be used to test correlations.

The distribution of continuous variables will be given as Mean, 95% confidence interval (CI) of the mean, standard deviation (SD), Minimum and Maximum (Mean (SD), (Min; Max)). The distribution of categorical and dichotomous variables will be given as number and percentage (n = (%)).

All subjects that consented to the investigation will be included in the safety population; all subjects enrolled and treated in the investigation will be included in the Intent-to-Treat (ITT) population. All subjects included in the investigation with no major protocol deviations will be included in the Per-Protocol (PP) population. The final decisions regarding the PP population will be taken after investigation completion, at the Clean File meeting before the database lock. All efficacy analyses will be performed on the PP population as main analysis. Complementary analysis for all efficacy variables will also be performed on the ITT population.

Details will be described in the Statistical Analysis Plan.

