#### **Missing data**

Handling of missing data will be described in the SAP. In order to minimize missing data, the importance of complete follow up data sets will be emphasized to investigators and investigation site staff, as will the importance of recruiting subjects who are motivated to undergo treatment and participate in the investigation. The investigation site is leading in the field of bone conduction devices, thus familiar with the outcomes of the treatment, and what level of treatment compliance that can be expected from patients considering undergoing treatment with a device. The sites will also have experience in conducting clinical investigations and recruiting investigation subjects. The patient information will give the subjects a clear understanding of the design of the investigation and the visit schedule. The latter has been carefully considered to mimic the standard practice of treatment with a bone conduction device, but also to be feasible in relation to the burden on the investigation subjects as a mitigation measure to avoid drop-outs and/or missing appointments. In addition, subjects will be given the opportunity to complete out PROs at the applicable site visits if they have forgotten to bring them or to complete them on beforehand.

Monitoring through the electronic data capturing system will be performed all through the investigation period. Early and close monitoring of the eCRFs will enable the Sponsor to take action and get back to site if missing data and/or deviations are found. The Sponsors representatives will be in close contact to site to give support and training for general quality assurance of the data captured in the investigation

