## 14 DEVIATIONS FROM CLINICAL INVESTIGATION PLAN

A CIP deviation is an intentional or unintentional failure to follow the requirements of the CIP. Every effort should be made to comply with the requirements of the CIP and the Investigator, and other representatives of the investigational site team, is not allowed to deviate from the CIP, unless needed to protect the rights, safety and well-being of the subjects (i.e., emergencies). Under these circumstances, deviations from the CIP may proceed without prior approval by the Sponsor and favourable opinion from EC. Such cases should be documented and reported to the EC, as per local requirements, and to the Sponsor as soon as possible, but in no event later than 5 working days after the emergency occurred.

If other deviations occur, the Investigator should inform the monitor/clinical trial manager and make a record in the CIP Deviation Log provided in the EDC system. The implications of the deviation must be reviewed and discussed between the Sponsor and the Investigator. If deviations are found during monitoring visits, they should also be documented in the monitoring report and handled as above. This should be done as soon as possible after detection to avoid repetitive deviations. Continuous review of protocol deviations during monitoring visits aim to detect systematic errors and to identify retraining needs at the site. Frequency of monitoring is described in the monitoring plan and should be increased if systematic deviations are identified. All protocol deviations must be documented stating the reason, date, the action(s) taken, and the impact for the subjects and/or the investigation. If serious or repeated deviations occur, the Sponsor has the right to initiate early termination of the investigation.

At the end of the investigation, or in connection to a predefined interim analysis, protocol deviations will be re-categorized as minor or major and their consequence on analysis populations will be determined.

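### Section 9.3.3 allows fitted subjects to be discontinued for undefined severe non-compliance or incorrect enrolment without obtaining Visit 2 outcomes, an avoidable risk of selective loss that the ITT analysis cannot repair

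*Combined protocol and SAP*

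**What the plan says.** Section 9.3.3 lists several routes out of the study: the subject's own decision, withdrawal by the investigator for safety or best interest, and, separately, "severe non-compliance to the CIP as judged by the investigator and/or the Sponsor, or incorrect enrolment". Incorrect enrolment is explained as meaning that "a subject did not meet the required inclusion/exclusion criteria for the investigation". One of those criteria is open-ended (section 9.3.2): "Subject deemed unsuitable for any medical or other reason as judged by PI or medical responsible". The section adds that "subjects withdrawing, discontinuing or being lost to follow-up from the investigation will not be replaced" and that "Collected data will be considered as far as possible in analyses". Discontinued subjects are to be asked for their reasons and about adverse events and, where possible, assessed by an investigator. No efficacy measurement is named.

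Deviators are also dealt with elsewhere. Section 14 requires every deviation to be logged with its reason and impact, and says that at the end or at the interim analysis "protocol deviations will be re-categorized as minor or major and their consequence on analysis populations will be determined". Section 11 drops subjects with major deviations from the PP set, which is the main efficacy set, and adds: "Complementary analysis for all efficacy variables will also be performed on the ITT population". Section 11.3 disregards missing values, in the same way for both sets.

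Table 2 and sections 9.4.1.2, 9.5.4.1 and 9.5.4.2 place the aided and unaided thresholds, the Sentio 1 SSQ12 and the preference form at Visit 2.

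**The concern.** Leaving the PP set and leaving the study are different things, and section 9.3.3 does not separate them. A major deviator who stays in the study leaves the PP set but keeps a Visit 2 result in the ITT set. A deviator who is discontinued before Visit 2 has no result for either set. The ITT analysis, which is there to show what happens when deviators are kept, then cannot show it.

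The direction of any effect is foreseeable. Section 9.1 expects a month of daily wear before Visit 2, so a subject who hardly uses the processor could be judged non-compliant, and dislike or small benefit is a plausible reason for low use. The study is unblinded, the judgement may be the sponsor's, and no lost subject is replaced. At stake are mainly the preference percentage (D1) and the SSQ12 difference (C3), where one or two people out of 12-14 count.

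**Working it through.** **1. Which endpoints are lost before Visit 2?** Functional gain (A1, B1), the Sentio 1 SSQ12 and its difference (C1, C3), preference (D1) and effective gain (E, which needs aided thresholds) all depend on Visit 2. Endpoint F, in-situ against conventional bone-conduction thresholds, is measured at Visit 1 (sections 9.4.1.1, 9.5.1 and 9.5.3.1) and is unaffected.

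**2. Do the safeguards recover the subject?** The ITT set formally includes every enrolled and treated subject, but under section 11.3 a missing value is disregarded there too. The promise to use collected data has nothing to act on for these endpoints. The deviation log records the loss but does not prevent it.

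**3. The plan's own sample size (section 11.1).** Inputs: 9 dB, SD 8 dB, 5% two-sided, 90% power.
- Normal approximation: n = (8 × (1.960 + 1.282) / 9)² = 8.30, so 9.
- Exact paired t-test: n = 11, with 91.8% power. This reproduces the stated 11.
- Drop-out: 11 / (1 − 0.15) = 12.9, so 13, inside the planned 12-14.
- Non-completers: 12 − 11 = 1 up to 14 − 11 = 3, counted over the whole 24 months.

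The sample size neither causes nor cures the problem.

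**4. Upper bound on the shift.** Assumption, not in the documents: every lost subject is the one with the worst result. The shift in the mean is the SD times the mean of the remaining standard normal order statistics (40,000 simulated trials), with SD 8 dB for gain and 0.9 for the SSQ12 difference, both from section 11.1. The preference counts are assumed, and all those lost are taken to be non-preferers.

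| Enrolled | Lost | Mean gain | SSQ12 difference | Preference |
|---|---|---|---|---|
| 12 | 1 | +1.2 dB | +0.13 | 9/12 = 75% to 9/11 = 82% |
| 13 | 2 | +2.1 dB | +0.23 | 9/13 = 69% to 9/11 = 82% |
| 14 | 3 | +2.8 dB | +0.31 | 10/14 = 71% to 10/11 = 91% |

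The planning values for comparison are 9 dB and 1 SSQ12 point. If loss is unrelated to outcome, the expected shift is zero.

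**5. Effect on the primary test.** Exact Wilcoxon signed-rank test, 2.5% in the favourable direction, normal differences.
- True gain 9 dB: rejection is 97% with all 14 analysed, 89% with 11 subjects and loss unrelated to outcome, and at least 99% with the 1, 2 or 3 worst of 14 removed. The conclusion is the same in nearly every trial.
- True gain 0 dB: 2.4% with all 14, rising to 7%, 15% and 26% with the 1, 2 or 3 worst removed. This is the extreme case and far from the planning value.

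**The case against.** A reader might infer that the clause lets poor users be removed and that the results are therefore biased towards Sentio 1. The documents do not support that. The stated triggers are severe non-compliance with the plan and failed eligibility; poor benefit and dislike are not among them, and the wording is permissive. Nothing shows that such subjects would do worse or would be removed selectively.

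There is also little information to act on before Visit 2. No minimum wear time is set, usage hours are recorded only for the current device at enrolment (section 9.5.2.1), and Table 2 schedules no contact between Visits 1 and 2. Section 12 says "Early and close monitoring of the eCRFs will enable the Sponsor to take action and get back to site if missing data", but its purpose is to repair data, and for the exposed endpoints the eCRF holds no Sentio 1 outcome before Visit 2. It would be wrong to say that removals are decided by people who already know those results.

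The sizes rest on assumed counts. The 1-3 expected non-completers cover two years and all causes. D1 has no hypothesis or success threshold, and its precision is low anyway: exact 95% limits are 43-95% for 9/12 and 48-98% for 9/11. Section 11 leaves population and missing-data detail to a statistical analysis plan, which might add protection. On the expected schedule (start 15 November 2022, 8 weeks of enrolment, Visit 2 at one month with up to one month's window), Visit 2 would have ended by about March 2023, before Revision 4 of 4 July 2023.

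All of this limits the point. What remains is that severe is undefined, that a low-use subject can come to light at an unscheduled visit or by the subject's own report, and that nothing in section 9.3.3 secures Visit 2 outcomes in that case.

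**Conclusion.** The point holds as a risk of selective loss that is cheap to avoid. Section 9.3.3 can end data collection between fitting and Visit 2 on a discretionary ground, and the complementary ITT analysis cannot bring the subject back. The exposed endpoints are preference and the SSQ12 difference. Under the worst-case assumption the shift is about 7 to 20 percentage points for preference and 0.13 to 0.31 points for SSQ12. Functional gain could shift by about 1 to 3 dB, but the primary conclusion hardly changes if the true gain is near 9 dB. Endpoint F is untouched. These sizes require that those lost are the worst responders; with loss unrelated to outcome there is no expected bias.

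**What to change.** In section 9.3.3, state that once Sentio 1 has been fitted, non-compliance or an eligibility error is logged as a deviation and does not by itself end data collection. With the subject's valid consent, and unless the investigator withdraws the subject for safety or best interest under the existing sentence, the planned Visit 2 thresholds, SSQ12 and preference form and the later adverse-event assessments are still obtained, whatever the device use. Exclusion from analysis then works only through the PP definition in sections 11 and 14. Say expressly that subjects without valid consent fall outside this rule, since signed consent is itself an inclusion criterion.

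If Visit 2 is already complete, report every post-fitting discontinuation with its reason and who decided it, and add a preference sensitivity analysis that counts such subjects as not preferring Sentio 1. In the first example above this returns 9/11 to 9/12. The amended text would then protect the safety follow-up to two years.

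Cost: one paragraph, with no new visit or procedure. The downside is that a few Visit 2 values from low-use or ineligible subjects enter the ITT set, which is what that set is for.

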#### *9.3.4 Subject Follow-up and Care*

After the investigation, the subjects will be receiving follow-up and care according to clinical standard procedures for patients with bone anchored implants and may be asked to participate in follow-up investigations.

[REDACTED]

[REDACTED]

#### *9.3.5 Number of Subjects*

It is planned to screen 16 subjects to reach enrollment of 12-14 subjects in this investigation. The sample

size has been based on a power calculation of the primary endpoint and is described in section 11.1.

Number of screened subjects:	16
Estimated number of enrolled subjects:	12-14
Estimated number of subjects completing the investigation:	11
Point of enrollment:	Visit 1
Point of balanced randomization:	NA
Total expected duration of the clinical investigation:	27 months
Expected duration of each subject's participation:	24 months (+/- 3 months)
Enrollment period:	8 weeks

#### 9.3.6 Information on vulnerable, pregnant and breastfeeding population, if applicable.

Pregnant and breastfeeding individuals will be offered to participate in the investigation as no risk in relation to usage of the investigational device for this population have been identified.

#### 9.4 Clinical Investigation flow chart

**Table 2. Flow chart of the investigation.**

Protocol activity	V 1	V2	V3	V4	Un-scheduled visit(s)
	Fitting	Follow up	Follow up	Follow up	
	0	1 month	1 year	2 years	
Subject Eligibility					
Informed consent	X				
Inclusion/exclusion criteria	X				
Demographics	X				
Audiological assessment & fitting					
Audiometry	X				
Fitting and/or adjustment of sound Processor	X	(X)	(X)	X	(X)
Sound field thresholds		X unaided X aided			
	X current device X Sentio 1				
PRO's					
SSQ12	X current device	X Sentio 1			
Preference		X Sentio 1			
Safety					
Adverse events assessment	X	X	X	X	X

#### 9.4.1 *Clinical Investigation visits*

##### 9.4.1.1 Visit 1 (screening/baseline visit)

Following procedures will be carried out during the first visit. The flow below is a suggested flow, based on convenience for subject and investigator the order may be changed. Information, informed consent and screening will always be carried out before any investigation related procedures are conducted.

- The subject is thoroughly informed about the investigation including all investigation related visits. Time will be given for consideration and answering any questions the subject might have.
- Consent form is signed.
- Screening according to inclusion and exclusion criteria.
- The subject's demographical data as well as their personal data and subjects' characteristics are registered.
- Audiometry is performed
- Fitting and adjustment of the Sentio 1 is performed
  - Including BC in-situ and feedback management measurement.
  - Strength of retention magnet is considered and potentially changed according to the subject's needs and preference.
  - Finetuning is considered and Sentio 1 is adjusted according to the subject's needs and preference.
- [REDACTED]
- Questionnaire for evaluation the subject's current hearing solution is filled out.
- Questionnaires for evaluation of the Sentio 1 is handed out and instructions to fill them out prior to next visit is given.
- AEs are assessed.

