### 8.2 Secondary Objective(s)

Secondary objective(s)	Corresponding secondary endpoint/outcome variable(s)	Section
B. To assess the improvement of hearing with the Sentio1.	1. Functional gain with Sentio 1, i.e., the difference in dB between unaided and aided sound field thresholds, for all measured frequencies.	9.5.3.2.1
C. To assess self-reported performance with the Sentio 1 compared to previous sound processor after at least one month field usage of the Sentio 1	1. Average SSQ12 scores with Sentio 1 for each question, sub-scales and in total. 2. Average SSQ12 scores with current sound processor for each question, sub-scales and in total.	9.5.4.1

	3. Difference in SSQ12 scores between Sentio 1 and current sound processor for each question, subscales and in total.	
D. To assess the preference of sound processor.	1. Percentage (%) of subjects who prefer the Sentio 1 over current sound processor	9.5.4.2
E. To assess the degree to which Sentio 1 compensates for the BC hearing loss	1. Effective gain defined as the difference in dB between aided sound field thresholds with Sentio 1 and unmasked BC thresholds on the aided ear(s). The effective gain is calculated for all measured frequencies. 2. Effective gain with Sentio 1, see definition above, calculated in average for frequencies 500, 1000, 2000 and 4000 Hz (PTA4).	9.5.3.2.2
F. To assess the difference between BC in-situ thresholds measured with Sentio 1 and conventional unmasked BC audiometry.	1. Difference in dB between Sentio 1 BC in situ thresholds and BC thresholds measured with conventional unmasked BC audiometry for the frequencies 500, 1000, 2000, 3000 and 4000 Hz	9.5.3.1 9.5.1
G. Assess safety with the Sentio 1 sound processor	1. Tabulation of AEs occurred throughout the investigation and percentage of individuals with reported AEs.	18

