### 9.5.3.3 [REDACTED]

### 9.5.4 Patient Related Outcomes (PRO)

#### 9.5.4.1 Speech Spatial and Qualities of hearing scale (SSQ)

[figure not shown]
A reduced version of the Speech, Spatial and Qualities of Hearing Scale (SSQ) questionnaire [3], the SSQ12,

	Title Clinical Investigation Plan BC114	Document no Doc-00117705	Revision 4	Page 24(39)
---	---	------------------------------------	----------------------	-----------------------

will be used in this investigation. The SSQ12 was developed and validated by Noble, Jensen [4] and contains 12 questions that reflect the perceived performance in speech intelligibility, spatial abilities, and sound quality. Each item is scored from 0 to 10, with larger values always indicating greater ability. The SSQ12 will be assessed at visit 1 (own device) and at visit 2 (Sentio 1).

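### The Visit 1 list places the only current-device SSQ12 after Sentio 1 fitting and lets the order vary, so the unblinded baseline for endpoints C2 and C3 may follow exposure to the new device

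*Combined protocol and SAP*

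**What the plan says.** Section 9.4.1.1 lists the Visit 1 steps. After consent, screening, demographics and audiometry comes "Fitting and adjustment of the Sentio 1 is performed", with the in-situ measurement, magnet choice and finetuning beneath it. A redacted step follows, and then "Questionnaire for evaluation the subject's current hearing solution is filled out". The list is not binding: "The flow below is a suggested flow, based on convenience for subject and investigator the order may be changed". One sequence is fixed: "Information, informed consent and screening will always be carried out before any investigation related procedures are conducted".

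Section 9.4.1.1 does not name the questionnaire. Table 2 and section 9.5.4.1 identify it: "The SSQ12 will be assessed at visit 1 (own device) and at visit 2 (Sentio 1"). No other current-device SSQ12 is scheduled.

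Section 8.2 builds two endpoints on that one assessment. C2 is "Average SSQ12 scores with current sound processor for each question, sub-scales and in total", and C3 is "Difference in SSQ12 scores between Sentio 1 and current sound processor for each question, subscales and in total".

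Section 9.1 describes the same visit in narrative form: "At the first visit the subject's current device is evaluated and Sentio 1 is fitted according to the audiological manual [D"]. It also says that the study cannot be blinded.

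**The concern.** C3 is a before-after comparison of unblinded self-reports, with one rating on each side. The baseline rating should describe the subject's own processor as it was experienced before the new one was tried. If it is given minutes after Sentio 1 has been fitted and tuned to the subject's liking, contrast with the new sound can move it. Because there is no second current-device rating, such a shift could be neither detected nor corrected.

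The free order adds a second, smaller difficulty. Some subjects may be rated before fitting and others after, and no visible text asks for the order to be recorded. Baselines taken in different orders are less comparable, in a study that expects about 11 completers.

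What is at stake is the reading of C2 and C3. Section 11.1 says that the sample size also supports conclusions on the SSQ12, so these endpoints are not incidental.

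**Working it through.** **1. Does the text fix the order?**

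- *Section 9.4.1.1:* fitting is listed before the current-device questionnaire. The order is free, apart from information, consent and screening.
- *Section 9.1:* evaluation of the current device is mentioned before fitting. The SSQ12 is not named and no sequence is required.
- *Table 2 and section 9.5.4.1:* these give the visit only, not the order within it.

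The visible text therefore allows either order, and its detailed list suggests the less favourable one.

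**2. The plan's own SSQ12 figure.** Inputs from section 11.1: difference 1, SD of the difference 0.9, two-sided 5%, 90% power, 11 completers.

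- Normal approximation: n = (0.9 × (1.960 + 1.282) / 1)² = 8.51, so 9.
- Power at n = 11: 95.8% by the normal approximation, 91.2% by the paired t-test, and about 88.2% by the exact Wilcoxon signed-rank test (the test named in section 11).

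Eleven completers are adequate on the plan's terms. The order of the questionnaire changes neither the sample size nor the nominal alpha.

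**3. What a shifted baseline would do to C3 (illustration).** The documents give no size, no direction and no count of subjects rated after fitting, so all three are assumptions here. The set-up is the exact two-sided Wilcoxon test with n = 11, rejecting if W ≤ 10 or W ≥ 56 (attained alpha 4.2%), with normal differences, SD 0.9 and 400,000 simulated samples per cell. Each exposed subject's difference moves by 0.2 / 0.3 / 0.5 points, **all in the same direction**.

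| Exposed | False-positive rate, true difference 0 (4.2% unshifted) | Power, true difference 1, shift against Sentio 1 (88.2% unshifted) |
|---|---|---|
| 11 of 11 | 8.8% / 14.8% / 34.3% | 71.1% / 59.5% / 34.4% |
| 6 of 11 | 5.4% / 6.9% / 11.4% | 79.7% / 73.9% / 59.5% |
| 3 of 11 | 4.4% / 4.7% / 5.6% | 84.3% / 81.6% / 75.5% |

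The bias in the mean difference is shift × (exposed / 11):

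- all 11 exposed: 0.20 to 0.50 points;
- 6 exposed: 0.11 to 0.27 points;
- 3 exposed: 0.05 to 0.14 points.

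For scale, the 95% confidence interval half-width is 2.228 × 0.9 / √11 = 0.60 points.

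**4. Mixed directions.** If all 11 are exposed but the sign differs between subjects, the false-positive rate for the same three shifts is 3.8% / 3.4% / 2.3% with a 6/5 split and 4.7% / 5.3% / 6.7% with an 8/3 split. Inflation is then small or absent.

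**5. Timing.** The planned start is 15 November 2022 (synopsis), with 8 weeks of enrolment and enrolment at Visit 1 (section 9.3.5). That puts the last Visit 1 at about 15 November + 56 days = 10 January 2023. Revision 4 is dated 04-07-2023.

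**The case against.** The strongest reply is that the list is only a suggestion, so the place of a bullet does not show what was done, and that section 9.1 puts the current device first. The first half stands. A reader might infer that every baseline was taken after fitting, and the documents do not support that. The second half stands only in part. Section 9.1 may reflect the intention, but if so it disagrees with the more detailed list, and the two need to be reconciled.

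A second reply is that the effect may be slight. The subjects already use their current device, and a short fitting in the clinic may hardly change how they rate it. Expectation raised by the study information is present in either order, so reordering removes only the contrast from the fitting itself. This is fair, and nothing in the documents contradicts it. A reader might infer that the comparison is tilted towards Sentio 1. The documents do not show that either, since the direction is unknown.

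A third reply is that error rates do not apply to C2, which is a descriptive average, and that section 8 states no hypothesis for C3. Both are true. The table in the working bears only on a test of C3 of the kind that section 11.1 contemplates.

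Finally, the redacted Visit 1 step, the audiological manual or the site worksheet mentioned in section 12 may already fix the order. If one of them does, a citation is enough.

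**Conclusion.** The point holds as a minor one. The visible text lets the sole current-device SSQ12 be taken after exposure to Sentio 1, its list suggests that order, and the order may differ between subjects. Whether this moved any rating, by how much and in which direction cannot be derived from the documents.

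A reader might take the 34% false-positive rate, or the fall in power to 34%, as the expected consequence. Each needs three assumptions together: the largest shift considered, all 11 completers exposed, and the same direction in every subject. With few exposed or mixed directions, the false-positive rate stays close to nominal.

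A reader might also infer that the study's conclusion is at risk. It is not. Section 8.1.1 rests success on the primary endpoint alone, which compares aided with unaided thresholds at Visit 2 and does not use the SSQ12. Nor is this a difference between sites, because the study has a single centre.

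**What to change.** 1. In section 9.4.1.1, list the current-device SSQ12 by name before the fitting step. Add it to the sentence on what must always come first: after consent and screening, before any exposure to Sentio 1. The remaining steps can stay flexible. Align section 9.1 with this.
2. If the audiological manual or the worksheet already sets this order, cite it in section 9.4.1.1 instead.
3. For visits already held, report from source documents, where recorded, how many subjects completed the questionnaire before fitting and how many after, or that the order was not recorded. State this as a limitation of C2 and C3. Keep it descriptive, with no test by order, in line with section 11.5.

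The cost of the first two steps is a wording change and slightly less scheduling freedom. No visit, procedure or subject is added. On the planned dates, Visit 1 was finished before revision 4, so for this cohort only the third step remains. It means looking up 12-14 records, and it yields a count only if the order or times were noted, which no visible text requires.
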